5.5.6 Collection of Human Biological Specimens

N/A

5.5.7 Banking of Human Biological Specimens

N/A

5.5.8 Study Time Line

- Study start-up: 1 October 2014
- Enrollment: For 12 months
- Interpretation of coronary CTAs: Within a month after all CCTAs have been enrolled and

performed

5.6 Investigational Drugs / Investigational Devices

N/A

5.6.1 Approval Status of Study Drugs

N/A

5.6.2 Approval Status of Study Devices

N/A

5.7 Statistical Considerations

The statistical evaluation will be performed as seen in the Data Analysis table below in 5.7.1. Of note, all outcomes compare the full and reduced scan groups.

5.7.1 Data Analysis Table

Aim 1- To assess the impact on CCTA image quality using modified calcium score approach.	
 - Image quality (4 point scale) - Signal/noise ratio 	
 - Treatment group - Treatment group 	
 - Two sample t-test or Mann-Whitney (dependent upon the distribution of the data). - Two sample t-test
Aim 2- To determine the rate of changes in the coronary CT angiography acquisition parameters of the modified versus standard calcium scoring	
 - Change in (increase or decrease) in tube current (mA) by 50 - Any change in tube potential (kV) - Change to/from retrospectively-gated CCTA - Any change in padding (acquisition window) - Changing to/from a high definition CT acquisition 	
 - Treatment group 	
 - Fisher's exact test

	All answered as yes/no		
Aim 3- To assess the difference in patient estimated effective radiation exposure (mSv) between the modified versus standard calcium scoring techniques.	- Average of radiation exposure (mSv)	- Treatment group	- Two sample t-test
Aim 4- To assess the difference in patient estimated effective radiation exposure (mSv) of the entire CCTA study (plus calcium scoring) between groups.	- Average of radiation exposure (mSv)	- Treatment group	- Two sample t-test

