5.7.2 Sample Size Estimation

The proposed sample size is 158 based on sample size calculations for aim 1, as described below.

Power and sample size for aim 1 is based on a standard deviation of radiation exposure of 3 to 3.5 mSv, based on clinical experience, and an anticipated 40% reduction in exposure from 4 to 2.4 mSv. A sample size of 154 (77 per group) will have 80% power to detect a difference in radiation exposure of 1.6 mSv if the standard deviation is 3.5, based on a t test for independent samples with a 5%, two-sided significance level.

Examining power analyses for a noninferiority studies, assuming that the full and reduced methods will produce similar outcomes for image quality and any change in CCTA parameters:

--For the comparison of image quality (aim 1), it is assumed that the image quality for the full method will be 3.2 (standard deviation = 1.1). This study will have power of 80% to show that the mean for the reduced method is at least as high as the mean for the full method. This assumes that the mean image quality scores for the full and reduced populations are 3.20 and 3.15 respectively, with a common within-group standard deviation of 1.10, that a difference of 0.49 points or less is unimportant, that the sample size in the two groups will be 79 and 79, and that

alpha (1 tailed) is set at .05. To accrue complete data 158 subjects, a total of sample size of up to 175 will be recruited to account for a 10% dropout rate for technical difficulties.

--This study will have 81% power to show that the event rate (event rate = any change in CCTA parameters) for the reduced method is at least as low as the event rate for the full method. This assumes that the event rates for the full and reduced method populations are precisely equal (at 50.0%), that a difference of 20% points or less is unimportant, that the sample size in the two groups will be 79 and 79, and that alpha (1 tailed) is set at .05.

While a 20% difference is relatively large, to detect a smaller difference between groups (i.e. difference of 10-15%) using the same assumptions, would require hundreds of subjects.

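### The primary image-quality comparison (and, secondarily, the rate of parameter changes) is sized for non-inferiority, but the margins in 5.7.2 are not carried into any analysis, interval or decision rule

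*Combined protocol and SAP*

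**What the plan says.** Section 5.7.2 introduces two of its calculations with "Examining power analyses for a noninferiority studies, assuming that the full and reduced methods will produce similar outcomes for image quality" and for parameter changes.

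- **Image quality** (primary endpoint in 5.8): means 3.20 (full) and 3.15 (reduced), SD 1.10, 79 per arm, one-tailed alpha 0.05, power 80%, and "that a difference of 0.49 points or less is unimportant". The stated goal is to show that "the mean for the reduced method is at least as high as the mean for the full method".
- **Parameter changes** (first secondary endpoint in 5.8): 50% in both arms, 79 per arm, one-tailed alpha 0.05, power 81%, and "that a difference of 20% points or less is unimportant". The endpoint is a composite ("event rate = any change in CCTA parameters").

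The analysis is set elsewhere. Section 5.7 states: "The statistical evaluation will be performed as seen in the Data Analysis table below in 5.7.1". Item 4 of 5.7.3 refers back to the same table for the primary and secondary endpoints. For quality, the table gives "Two sample t-test or Mann-Whitney (dependent upon the distribution of the data"). For Aim 2 it lists five yes/no items and Fisher's exact test. It states no margin, confidence interval, sidedness or decision rule. Item 5 of 5.7.3 adds an ordinal regression of the quality score, also without a margin.

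**The concern.** A non-inferiority conclusion needs a comparison against the margin. The margins stand only among the power assumptions, and the section that governs the analysis does not use them. A t-test can be run against a null shifted by 0.49, but the table does not say so. Mann-Whitney, which may replace it depending on the data, has no parameter that corresponds to a 0.49 difference in means. Fisher's exact test as listed tests equality, so a 20-point difference in rates does not enter it. Choosing one-sided versions of the listed tests would not help, because the margin would still be absent.

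At stake is the trial's main message: that a shorter, lower-dose pre-scan does not materially harm CCTA quality. The plan leaves open how that message would be drawn from the data, so the rule could be chosen after the results are known.

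**Working it through.** **1. The plan's own figures.** Inputs are from 5.7.2. For quality, SE = 1.1 × √(2/79) = 0.175. The distance from the assumed difference to the margin is 0.49 − 0.05 = 0.44, and 0.44/0.175 = 2.514. Normal approximation: Φ(2.514 − 1.645) = 80.8%. Noncentral t with 156 df and critical value 1.655: 80.5%. The plan states 80%.

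For the composite, SE = √(0.5/79) = 0.0796, and Φ(0.20/0.0796 − 1.645) = 80.8%. Exact enumeration of a Wald 90% interval gives 80.9%. The plan states 81%.

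Both figures reproduce only as comparisons against the margins. The calculation that opens with "Power and sample size for aim 1 is based on a standard deviation of radiation exposure of 3 to 3.5 mSv" is a separate two-sided test of a difference. It gives 154 subjects, so the 158 comes from the quality calculation.

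**2. Two criteria for quality.** With 79 per arm, t(0.95) = 1.655 and t(0.975) = 1.975:

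- Non-inferiority is shown if the observed deficit is below 0.49 − 1.655 × SE.
- A two-sided 5% t-test of equality is non-significant if the deficit is below 1.975 × SE. Two-sided is my assumption, since the table gives no sidedness.

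The fifth column is the probability that the t-test is non-significant when the true deficit is 0.49 (noncentral t, noncentrality 0.49/SE). The last column is the power of the non-inferiority rule at a true deficit of 0.05. Only SD 1.1 is from the plan; the other values show the range.

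| SD | SE | Non-inferior if deficit below | t-test non-significant if deficit below | Non-significant at true deficit 0.49 | Power of margin rule |
|---|---|---|---|---|---|
| 0.7 | 0.111 | 0.306 | 0.220 | 0.8% | 98.9% |
| 0.85 | 0.135 | 0.266 | 0.267 | 5.0% | 94.5% |
| 1.1 | 0.175 | 0.200 | 0.346 | 20.5% | 80.5% |
| 1.3 | 0.207 | 0.148 | 0.409 | 34.7% | 68.2% |

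At SD 1.1, an observed deficit between about 0.20 and 0.35 is non-significant yet fails the margin. Near SD 0.85 the two criteria coincide. At SD 0.7 the mismatch reverses: a deficit between about 0.22 and 0.31 is significant yet non-inferior. A one-sided 5% t-test against zero would still be non-significant 12.7% of the time at SD 1.1 and a true deficit of 0.49.

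**3. Composite of parameter changes.** By exact binomial enumeration with 79 per arm and true rates of 50% and 70%, Fisher's test is non-significant 32.4% of the time two-sided and 22.1% one-sided. As an example, take 40/79 in the full arm. Fisher's test stays non-significant up to 53/79 in the reduced arm (13/79 = 16.5 points; p = 0.052). The 90% interval excludes +20 points only up to 45/79 (5/79 = 6.3 points).

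**4. Direction of the composite.** If the rates were 50% (full) and 30% (reduced), a rule on the upper limit alone would pass more than 99.9% of the time.

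**The case against.** The strongest reply is that the margins, one-tailed alpha, direction and arm sizes are all in 5.7.2, under the same section 5.7 as the table, and that a t-test is listed. Read together, they give most of a shifted one-sided t-test. That stands in part: a reader might infer that the plan has no margin or non-inferiority hypothesis at all, and the documents do not support that. What is missing is the link from those inputs to the analysis and the rule for concluding. The inference also fails for Mann-Whitney and for Fisher's test, and the goal worded in 5.7.2 (at least as high) is not the hypothesis that a 0.49 margin defines.

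A reader might also infer that the trial will claim similarity from a non-significant result, with a 20.5% or 32.4% error rate. The plan does not say so. Those figures are conditional on that reading, and the first also depends on SD 1.1. The SD of the per-patient mean of segment scores is not given; at about 0.85 or below, the excess error disappears.

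It can further be said that the choice of quality score is already settled. Largely it is: the CCTA interpretation text in 5.5 defines overall patient quality as the mean of the consensus segment scores. Naming that score in the table is a clarification. Differences between the lists of parameter changes, and the aim 1 label on the radiation calculation, are clerical and not part of this point.

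**Conclusion.** The mismatch holds and should be fixed before analysis, mainly because it affects the primary endpoint. It does not depend on SD or on any misuse: at SD 1.1 the listed t-test is more lenient than the powered criterion if non-significance is taken as success, and at SD 0.7 a significant result can lie within the margin. The plan has no rule for either case. The sample-size arithmetic is sound. The Aim 2 part is secondary; its figures rest on the plan's 50% rate and 79 per arm.

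**What to change.** **Main change (5.7.1, Aim 1).** Report the difference in mean patient-level consensus quality score (the segment mean defined in 5.5; reduced minus full) with a two-sided 90% confidence interval. Conclude non-inferiority on image quality only if the lower limit is above -0.49. Keep Mann-Whitney as supportive only. Leave the quantitative measures (signal, noise, contrast-to-noise), which 5.8 also makes primary, as planned. In 5.7.2, replace the at-least-as-high wording with *not more than 0.49 points lower*.

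**Secondary change (5.7.1, Aim 2).** Name the composite of any parameter change as the powered endpoint and report the risk difference (reduced minus full) with a two-sided 90% interval. Under the plan's own direction, conclude non-inferiority only if the upper limit is below +20 points. The sponsor should confirm that direction, because an upper limit alone would also pass a reduced scan that prompts far fewer changes. Reporting both limits makes this visible. Keep Fisher's tests for the individual items.

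**Cost.** Text only: N stays at 158 complete and up to 175 recruited. Power is 80.9% for the composite, and 80.5% for quality if SD 1.1 refers to the segment-mean score (98.9% at SD 0.7, 68.2% at SD 1.3), so the sponsor should confirm which score that SD describes. The 90% interval matches the plan's one-tailed 0.05. A 95% interval would lower power to about 70% for quality and 71% for the composite, and restoring 80% would take 99 per arm.

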All CT examinations will be performed on standard multi-detector CT machines typically utilized for CCTA, in accordance with SCCT guidelines. Prior to any imaging, both the radiologist and cardiologist (non-study personnel) clinically performing the CCTA will fill out a form choosing their initial proposed CCTA acquisition parameters (type of gating, mA, kV, padding, use of high-definition scanning) based on the patient’s age, sex, BMI and achieved pre-scan heart rate, as is typical of all CCTA examinations. Then antero-posterior and lateral topograms of the chest will be obtained to plan subsequent data acquisition, as required for all CCTA examinations. Based on randomization, either a modified or standard calcium scoring series will be performed: Subjects will be randomized in a 1:1 ratio to either modified or standard calcium scoring using a computer program based on random number generation. Assignments will be concealed in sequentially numbered opaque sealed envelopes (SNOSE). The randomization assignment and envelopes will be prepared by a person who is not involved

in the recruitment process or clinical conduct or interpretation of the non-contrast studies or CCTA.

In patients randomized to standard coronary artery calcium scoring, this scan will be performed in usual axial fashion obtained at 70% of the R-R interval using the following parameters: rotation time 0.35 sec; collimation of 64 x 0.625mm; detector coverage of 20.0 mm; axial thickness 2.5; tube voltage, 120 kV and tube current 250mA. The scan length, in accordance with current protocol, will be from 1 cm below the carina through the diaphragms.

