5.7.3 Data Analysis Plan

1. A patient flow diagram as per CONSORT guidelines will be provided to present the number of subjects recruited, screened, refusals or subjects excluded (with reasons), randomized, lost to follow up, etc. Beginning and ending months of recruitment will be described.
2. A table of baseline demographic and clinical characteristics will be presented for the full and reduced scan groups to include means with standard deviations for continuous normally distributed variables, medians with interquartile ranges for ordinal data and counts with percentages for categorical data. Groups may be compared using two sample t-tests, Wilcoxon rank sum tests or Fisher's exact test as appropriate.
3. Interrater reliability for quality scores will be examined using the Kappa statistic.
4. Univariate comparison of the primary and secondary endpoints are described above in the Data Analysis table.
5. Multivariate analysis of the quality score will include ordinal regression, with the concensus quality score (on a scale from 1 to 4) as the dependent variable and the independent variables to include demographic and clinical factors known to affect CCTA quality, such as BMI, breath-holding, resting heart rate, use of nitroglycerin, etc.

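### Aim 4 compares whole-study radiation dose without adjustment, although predictors of that dose are recorded before the arm is revealed; adjusting for them would add precision at almost no cost

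*Combined protocol and SAP*

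**What the plan says.** - **Test for dose.** In section 5.7.1, Aims 3 and 4 share the outcome "Average of radiation exposure (mSv"), the single explanatory variable treatment group, and a two-sample t-test. The distribution-dependent choice "Two sample t-test or Mann-Whitney (dependent upon the distribution of the data") is offered only for the image-quality score in Aim 1.
- **No adjustment.** Section 5.7.3, item 4: "Univariate comparison of the primary and secondary endpoints are described above in the Data Analysis table". The one covariate model, in item 5, is for another outcome: "Multivariate analysis of the quality score will include ordinal regression".
- **Planning figures.** Section 5.7.2 assumes a "standard deviation of radiation exposure of 3 to 3.5 mSv" and "an anticipated 40% reduction in exposure from 4 to 2.4 mSv", and states that "A sample size of 154 (77 per group) will have 80% power to detect a difference in radiation exposure of 1.6 mSv" at SD 3.5, two-sided 5%. The paragraph is labelled aim 1, although it concerns dose, and it does not say whether it describes the calcium scan (Aim 3) or the whole study (Aim 4).
- **Covariates in hand.** Under CT Protocol in section 5.5, the radiologist and cardiologist write down, before any imaging, their "initial proposed CCTA acquisition parameters (type of gating, mA, kV, padding, use of high-definition scanning"). The Methods text says they look at the allocation card only after that decision. Section 5.5.5 puts height and weight on the patient sheet, and gating, padding, tube current and tube voltage on the CT sheet, both before and after calcium scoring.

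**The concern.** Only the calcium scan differs between arms by design. In Aim 4 that difference has to be seen against patient-to-patient variation in CCTA dose. Section 4.1 lists acquisition mode, tube potential and tube current among the settings an imager changes to lower the dose of the angiogram, so the proposed values should explain part of that variation. They are fixed before allocation is known, so adjusting for them cannot bias the comparison by conditioning on a consequence of the arm. An unadjusted t-test leaves that variation in the error term. What is at stake is the width of the confidence interval for the whole-study saving, and the chance of missing a real one.

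The planning figures also point to a right-skewed dose distribution, which bears on how the interval is computed and on whether a second summary is useful.

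**Working it through.** **1. Reproduce the plan's figure.** Inputs from section 5.7.2: difference 1.6 mSv (4 − 2.4), SD 3.5, two-sided 5%, 80% power.

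- Normal approximation: n per arm = 2 × (1.960 + 0.842)² × (3.5/1.6)² = 2 × 7.85 × 4.785 ≈ 75.1, rounded up to 76.
- Noncentral t: 76.09, rounded up to 77. Power is 80.5% at 77 per arm and 81.5% at 79 per arm, the evaluable size behind the total of 158.

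The stated 77 per group is reproduced.

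**2. Effect of adjustment on the same scale.** If pre-randomisation covariates explain a fraction R² of within-arm variance, the residual SD is 3.5 × √(1 − R²). The mean difference of 1.6 mSv is unchanged. Power is by noncentral t at 79 per arm, and n per arm for 80% power is by normal approximation. The documents give no R², so a range is shown.

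| R² (assumed) | Residual SD (mSv) | 1.6 / residual SD | Power at 79 per arm | n per arm for 80% |
|---|---|---|---|---|
| 0 | 3.50 | 0.457 | 81.5% | 76 |
| 0.1 | 3.32 | 0.482 | 85% | 68 |
| 0.2 | 3.13 | 0.511 | 89% | 61 |
| 0.3 | 2.93 | 0.546 | 93% | 53 |
| 0.5 | 2.47 | 0.646 | 98% | 38 |

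At the lower planning SD of 3.0, unadjusted power is already 91.5%, and R² of 0.1 to 0.5 takes it to 94–99.7%. These figures ignore the degrees of freedom spent on covariates. With five single-term covariates the error degrees of freedom fall only from 156 (158 − 2) to 151.

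**3. Skew.** Dose cannot be negative. A normal distribution with the planning figures would put Φ(−4/3) to Φ(−4/3.5) = 9–13% of the standard arm below zero, and Φ(−2.4/3) to Φ(−2.4/3.5) = 21–25% of the modified arm. Doses with these moments must be right-skewed.

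**4. Does skew invalidate the raw test?** No. In simulation (20,000 trials, 79 per arm, lognormal or gamma, mean 4, SD 3 or 3.5), the raw t-test rejects 4.7–5.2% of the time under the null.

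**5. Would a log-scale test be better?** It depends on the unknown shape. Simulated power at 79 per arm, means 4 and 2.4:

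| Dose model | Raw t | Log t |
|---|---|---|
| Lognormal, SD 3.5 in both arms | 83% | >99% |
| Lognormal, constant CV (SD 3.5 falling to 2.1) | 95% | 99% |
| Gamma, constant CV | 95% | 85% |

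The first row flatters the log test. Holding SD at 3.5 while the mean falls gives log SDs of 0.754 and 1.068 and geometric means of 4·exp(−0.754²/2) = 3.01 and 2.4·exp(−1.068²/2) = 1.36. Their ratio is 0.45, a 55% reduction and not the planned 40%. The log test also answers a different question: with equal mean doses of 4 mSv and lognormal SDs of 3.5 and 2.1, it rejects 36% of the time, against about 5% for the raw test.

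**6. Which aim do the planning figures fit?** Section 4.1 puts a calcium scan at 1–3 mSv, and section 5.5 runs it at one kV and one mA setting per arm. A mean of 4 with SD 3–3.5 cannot describe that scan. With an assumed calcium-scan SD of 0.5–1 mSv, a 0.8 mSv difference has over 99% raw power at 79 per arm.

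**The case against.** The strongest reply is that nothing is broken. The t-test holds its level and delivers its stated 80%, and whole-study dose is a secondary endpoint (section 5.8). All of that stands.

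The size of the gain is also uncertain. R² is assumed, and an SD of 3–3.5 mSv sits poorly with the approximately 2–8 mSv that section 6.2 gives for total exposure. With an assumed SD of 1.5–2 mSv, a 1.6 mSv difference already has over 99% power unadjusted. This limits the gain, but two things remain. The sponsor itself planned on SD 3–3.5, and the full 1.6 mSv saving is not assured: where a standard calcium scan gives only 1 mSv, the scan itself cannot save that much. A simulated saving from 1.0 to 0.3 mSv, with CCTA dose at an assumed mean of 4, leaves the raw test at 59–83% power for CCTA SDs of 2 down to 1.5, and at 26% for SD 3.5.

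A reader might go further and infer that both dose aims should move to log(mSv) as the main analysis. The documents do not support that. Sections 3 and 5.7.1 ask about the difference in mSv, and section 6.2 ties cancer risk to cumulative exposure, for which the arithmetic mean is the relevant summary. High-dose scans cannot be treated as noise either: a switch to or from retrospective gating after the calcium scan is an Aim 2 outcome, so such scans may be an effect of the arm. Nor can the skew argument be carried over to Aim 3, because the planning figures do not fit a calcium scan.

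**Conclusion.** The point holds for Aim 4 as a matter of efficiency. The plan leaves whole-study dose unadjusted while suitable covariates, fixed before the arm is known, are already collected. Under the plan's SD of 3.5 and difference of 1.6 mSv, adjustment takes power at 79 per arm from 81.5% to 85%, 89% or 98% for R² of 0.1, 0.2 or 0.5. This rests on the assumed R², on the planning SD applying to whole-study dose, and on the pre-scan forms being complete. If the true SD is much smaller and the saving is 1.6 mSv, there is little left to gain.

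The skew implied by the planning figures justifies a robust interval and a supportive ratio. It does not justify replacing the mean difference. The planned t-test is neither invalid nor underpowered for its stated target, and no case is made for changing Aim 3.

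**What to change.** In section 5.7.1, for Aim 4 only, before the data are analysed by arm:

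- Keep the mean mSv difference as the main estimate. Obtain it from a linear model with treatment group, BMI and the pre-scan proposed gating, kV, mA and padding, and report it with a robust-SE or bootstrap 95% CI.
- State that only values recorded before the calcium scan enter the model. The post-scan values may be changed by the randomised scan, so adjusting for them would remove part of the effect under study.
- Add the ratio of geometric means from log(mSv) as a supportive analysis, labelled as a different quantity.
- In section 5.7.2, say which aim the dose calculation serves.

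The cost is a change of wording and slightly more analysis work, with no new data or patients. The analysis does come to depend on complete pre-scan forms, so name in advance how a missing form is handled and report the unadjusted difference alongside.
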